7.2 PARTICIPANT DISCONTINUATION/WITHDRAWAL FROM THE STUDY

Prior to removal from study, effort must be made to have all subjects complete a safety visit approximately 14 days (+14 days) following the last dose of study therapy. Participants are free to withdraw consent at any time upon request. Participants may also choose to withdraw treatment but remain in the study for follow up. Participants must be withdrawn consistent with Section 6.1.2. Additionally, the PI or Medically Responsible Investigator may also choose to withdraw treatment or withdraw a participant from the study based on clinical or professional judgement. An investigator may withdraw treatment or a participant from study for the following reasons:

- Request by participant to be withdrawn from the study.
- Flares not resolving within 28 days or if, in the opinion of the medically-responsible investigator, the participant requires immediate immunosuppressive therapy that is not allowed in the protocol.
- Any Grade 4 adverse event that is unexpected and at least possibly related to study drug.
- More than 45 days delay in treatment after the screening visit.
- More than one (1) "no-show" for a visit.
- Persistent elevation of LFTs of > 2 times upper limit of normal persistently present on repeated samples 14 days +/- 7 days apart.

- >30% increase in serum creatinine from baseline at enrollment, persistently present on repeated samples 14 days +/- 7 days apart.
- Increase in proteinuria at the time of screening visit to protein to creatinine ratio of more than 1.000 mg/dL or more than 1000 mg in a 24 hours urine collection, persistently present on repeated samples 14 days +/- 7 days apart.
- Any other reason that, in the opinion of the responsible Investigator or Medically Responsible Physician, poses unacceptable risk to the participant.
- Infections requiring intravenous antibiotic treatment.
- Development of any malignancy.
- Urine BK virus level of more than 10 million copies/ml by quantitative PCR or detection of BK virus in serum by quantitative PCR.
- Non-compliance with treatment (<80% compliance by pill count).

The reason for participant discontinuation or withdrawal from the study will be recorded on the Voluntary Study Withdrawal Case Report Form (CRF). Participant who signs informed consent and are randomized, but do not receive the study drug, may be replaced.

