Participants who sign informed consent, and are randomized and receive the study intervention, and subsequently withdraw, or are withdrawn from the study, will be replaced.

A Participant is considered to have completed the study when he/she has completed 168 days of treatment with Tofacitinib and the day 196 follow-up assessments.

Participants randomized to a study arm who withdraw from the trial prior to starting on study drug will be replaced. Participants who withdraw study treatment and/or withdraw from the trial for any reason other than drug related adverse events after initiating the first dose of Tofacitinib and before completing 112 doses of Tofacitinib (study day 56) will also be replaced in order to maintain the sample size of 20 participants on Tofacitinib and 10 participants on placebo, for total of 30 evaluable participants. Based on experience with studies in SS participants, we expect a withdrawal rate of approximately 25% and therefore plan for a target enrollment of 30 participants plus 11 participants in event of participant withdrawal.

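### Section 7.2 gives two incompatible replacement rules, and the follow-up condition in Section 9.2.1 could drop a toxicity withdrawal from the primary denominator

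*Combined protocol and SAP*

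**What the plan says.** Section 7.2 of the combined protocol and SAP deals with replacement more than once.

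- **Dosed participants, no limit:** those consented and randomised who "receive the study intervention, and subsequently withdraw, or are withdrawn from the study, will be replaced".
- **Dosed participants, limited:** two paragraphs later, drug-related adverse events are carved out as a reason, and people who stop treatment or leave early for other causes "before completing 112 doses of Tofacitinib (study day 56) will also be replaced". The stated purpose is to hold 20 on tofacitinib and 10 on placebo, a total of 30 participants called evaluable.
- **Undosed participants:** "Participant who signs informed consent and are randomized, but do not receive the study drug, may be replaced", and later "Participants randomized to a study arm who withdraw from the trial prior to starting on study drug will be replaced".

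The same section expects about 25% withdrawal and plans 30 participants plus 11. Section 4.1 gives the 11 as a maximum and uses it both for attrition or early withdrawal and for filling incomplete randomisation blocks.

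Some withdrawal reasons in Section 7.2 can be drug toxicity, for example "Any Grade 4 adverse event that is unexpected and at least possibly related to study drug". The primary endpoint in Section 3 is safety and tolerability, with toxicity defined as a drug-related event of Grade 3 or above. Section 9.3.2 summarises it in the safety population. Section 9.2.1 defines that population by two conditions, at least a partial dose and a completed safety follow-up, and includes premature withdrawals.

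**The concern.** The two rules for dosed participants treat the same person differently, and nothing in Section 7.2 or Section 4.1 says which governs. The difference falls on the people who matter most to a safety trial. The limited rule exempts drug-related withdrawals from replacement, and the unlimited one removes that exemption.

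The number randomised, the number exposed to drug and the meaning of 30 evaluable participants all depend on which sentence the site follows. If toxicity withdrawals could also fall out of the set on which toxicity is reported, the primary result would be understated.

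**Working it through.** **1. The rules side by side.** At two doses a day, 112 doses take 112/2 = 56 days, so the Day 56 gloss is consistent.

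| Participant after first dose | Unlimited rule | Limited rule |
|---|---|---|
| Leaves study before 112 doses, not drug-related | replaced | replaced |
| Leaves study before 112 doses, drug-related event | replaced | not covered |
| Leaves study after Day 56, any reason | replaced | not covered |
| Stops treatment before 112 doses, not drug-related, stays in study | not covered | replaced |

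The rules agree only in the first row.

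**2. Reproducing the planned 41.** The inputs from Section 7.2 are 30 evaluable (20 + 10) and withdrawal d = 0.25. The number to randomise is n/(1 − d).

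- Overall: 30/0.75 = 40.
- By arm, rounded up: 20/0.75 = 26.7, so 27; 10/0.75 = 13.3, so 14; total 41 = 30 + 11.
- The alternative 30 × 1.25 = 37.5, rounded up to 38, does not reproduce it.

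The stated 41 is therefore not an error. It is the number obtained when every withdrawal is replaced.

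**3. The limited rule.** Let s be the share of withdrawals that are both before 112 doses and not drug-related. The documents do not give s, so a range is assumed. The number to randomise is n/(1 − 0.25s).

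| s (assumed) | Overall | By arm, rounded up |
|---|---|---|
| 0.75 | 30/0.8125 = 36.9, so 37 | 25 + 13 = 38 |
| 0.50 | 30/0.875 = 34.3, so 35 | 23 + 12 = 35 |
| 0.25 | 30/0.9375 = 32 | 22 + 11 = 33 |

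The margin also differs. With 41 randomised and independent withdrawals, the chance of at least 30 not needing replacement is 0.68 under the unlimited rule. It is 0.997 under the limited rule at s = 0.50.

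**4. The denominator.** Section 9.2.2 keeps everyone randomised and dosed in the ITT set. Section 9.2.3 makes participants evaluable for toxicity from the first dose. Section 9.2.1 keeps early withdrawals but adds the follow-up condition. Section 7.2 asks only for an effort to obtain a safety visit about 14 days after the last dose.

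As an illustration, suppose three tofacitinib participants are withdrawn for toxicity and no one else has a toxicity.

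- All dosed kept: 3/(20 + 3) = 13.0% if the three are replaced, 3/20 = 15.0% if not. All three count either way.
- One of the three misses the safety follow-up and is excluded: 2/22 = 9.1% if replaced, 2/19 = 10.5% if not.

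The loss comes from the follow-up condition and arises under either replacement rule.

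**The case against.** The best defence of the text is that the limited rule lists further cases and never says that others are not replaced. That reading fails for study withdrawals. The limited rule names them explicitly, and its limits on reason and timing would then do nothing for them.

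The defence is stronger on consequences. A reader might infer that replacement clears toxicity cases out of the analysed set, so that in the illustration the drug arm would show 0/20. The documents do not support this. No analysis uses an evaluable set, the figure of 30 is an enrolment target, and Section 9.2 retains dosed early withdrawals. It is also no gap that Section 7.2 is silent on analysis sets, since Section 9.2 is where they are defined.

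Other tempting readings also go too far:

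- **That the 11 places prove the unlimited rule was intended.** Section 4.1 makes 11 a ceiling and also spends it on unfilled blocks. It is a best match only.
- **That the limited rule would leave Day 168 data only on those who never withdraw.** Sections 6.4 and 8.2.2 ask participants withdrawn after dosing to return for Days 168 and 196.
- **That counting doses of tofacitinib excludes the placebo arm.** The same sentence aims to keep 10 on placebo, and Section 6.3 blinds the investigators. This is loose wording.

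The inconsistency over undosed participants cannot affect the ITT or safety results, since both sets require a dose. The sample size is described as arbitrary in Section 9.1.1 and Section 9.1 plans no formal inference, so a few participants more or fewer has limited inferential weight.

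The return visits also reduce the risk in Section 9.2.1, but they do not remove it. They are requests, and someone who leaves because of toxicity may decline them.

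**Conclusion.** The contradiction is real and no other section resolves it. At the plan's 25% withdrawal, the rules imply 40 to 41 randomised against roughly 32 to 38. The second range rests on the assumption that 25% to 75% of withdrawals would qualify. The stated 30 + 11 stands as arithmetic.

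Replacement alone does not bias the toxicity rate. The remaining risk to the primary endpoint is narrower: a toxicity withdrawal without a completed safety follow-up does not meet the definition in Section 9.2.1. Its size depends on how many such participants there are, which the documents cannot tell us. With about 20 on drug, one lost case out of three would move the rate by roughly four percentage points (13.0% to 9.1%, or 15.0% to 10.5%). The point is worth correcting because the trial is small, safety is its primary purpose and the correction is cheap.

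**What to change.** 1. In Section 7.2, reconcile the sentences into one replacement rule for dosed participants, with its limits on reason and timing, if any, stated once. Say whether stopping treatment while staying in the study counts. Word it for study drug so that it plainly covers both arms.
2. Use one verb for undosed participants.
3. Restate the number of extra places so that it follows from the rule kept, showing separately any places reserved for unfilled blocks. Define the 30 evaluable participants or call them an enrolment target.
4. State in Sections 7.2 and 9.2.1 that every dosed participant, replaced or not and with or without a completed safety follow-up, stays in the safety denominator.

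The cost is a short amendment and, if the limited rule is kept, possibly fewer completers. The version is dated 07/01/2024 and the synopsis gives an end date of 09/20/2024, so few enrolment decisions may remain. If enrolment has closed, record which rule was followed and how many participants were replaced. Item 4 is still useful at that stage, provided it is settled before database lock and unblinding.

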7.3 LOST TO FOLLOW-UP

A participant will be considered lost to follow-up if he or she fails to return for two (2) scheduled visits and is unable to be contacted by the study site staff.

The following actions must be taken if a participant fails to return to the clinic for a required study visit:

- The site will attempt to contact the participant and reschedule the missed visit within 7 days and counsel the participant on the importance of maintaining the assigned visit schedule and ascertain if the participant wishes to and/or should continue in the study.
- Before a participant is deemed lost to follow-up, the investigator or designee will make every effort to regain contact with the participant (where possible, 3 telephone calls and, if necessary, a certified letter to the participant's last known mailing address or local equivalent methods). These contact attempts should be documented in the participant's medical record or study file.

Abbreviated Title: Tofacitinib in Sjögren's syndrome

Version Date: 07/01/2024

- Should the participant continue to be unreachable, he or she will be considered to have withdrawn from the study with a primary reason of lost to follow-up.

8 STUDY ASSESSMENTS AND PROCEDURES

8.1 STUDY ASSESSMENT AND PROCEDURE SCHEDULING

All the procedures and assessments explained below may be completed within the visit window period -45 days for the screening visit and +/- 7 days for follow up visits to accommodate scheduling and to reduce burden to participants (i.e., flexibility to optimize time in clinic to accommodate patient preferences).

8.1.1 STUDY PHASES

PRE-SCREENING VIA PROTOCOL: 15-D-0051

Participants will be pre-screened on the "Characterization of Diseases with Salivary Gland Involvement" protocol (15-D-0051). Those with mild-to-moderately active primary SS and no obvious exclusion criteria will be offered the chance to enroll in 20-D-0131.

NIH participants with SS who are identified from either Protocol 11-D-0172 or Protocol 15-D-0051 will be offered participation in the study if they are found to have mild to moderate disease activity and no obvious exclusion criteria. Pre-screening assessments will be done during routine clinical follow up or initial evaluations and will include review of medical history, physical examination and laboratory assessment and concomitant medications. All participants referred to this study will be enrolled to protocol 15-D-0051.

Screening Period (-45 days to Day 1):

Participants may be scheduled for screening visits at the NIH Dental clinic, NIH Outpatient 9 Clinic or the 5SWS Day Hospital. Screening procedures will be performed as part of this study. Any protocol mandated screening parameter greater than 30 days from screening visit must be repeated for the screening visit. Subjects will be asked to fast on the day of the appointment and to avoid taking saliva stimulants 24 hours prior to the appointment.

The following procedures will be done during the Screening Period:

- Informed Consent
- Review of inclusion and exclusion criteria
- Medical history and physical examination,
- Vital sign measurements,
- Dental history,
- Oral, and Head and Neck examinations,
- Saliva Collection
- Saliva Flow rates
- Salivary Gland Ultrasound,
- Comprehensive Ophthalmologic Exam
 - Vision exam
 - Intraocular pressure (IOP)
 - Dilated exam (fundoscopy)
 - Schirmer's test with and without anesthesia

Abbreviated Title: Tofacitinib in Sjögren's syndrome

Version Date: 07/01/2024

- Ocular surface staining (Fluorescein, Lissamine green)
- EKG
- Concomitant medications review
- Minor Salivary Gland Biopsy. (If participants were previously seen on 15-D-0051 within the last twelve months and the appropriate minimum necessary tissues and research studies were procured, this biopsy may be used as the baseline biopsy).
- Assessment of SS activity: ESSDAI, PGA
- Laboratory studies:
 - Complete blood count with differential,
 - Serum chemistry panel (creatinine, glucose, urea nitrogen, total bilirubin, alanine aminotransferase, aspartate aminotransferase, alkaline phosphatase, albumin),
 - Pregnancy test (serum or urine; for females with reproductive potential only),
 - Urinalysis and random urine protein/creatinine ratio,
 - Lipid panel: LDH (low density lipoprotein), HDL (high density lipoprotein), TG (Triglycerides), Total cholesterol
 - Lipoprotein Profile: Apolipoprotein A-1, Apolipoprotein
 - ANA and anti-ENA panel (anti-RNP, anti-SmRNP, anti-SSA, anti-SSB), anticardiolipin antibodies, lupus anticoagulant, and anti-beta2-glycoprotein antibodies, anti-dsDNA antibodies,
 - Serum complement components C3 and C4
 - Quantitative Immunoglobulins: IgA, IgG, IgM
 - Serum protein electrophoresis (SPEP)
 - Screening serologies for hepatitis B, hepatitis C and HIV (per NIH lab each of these tests may only be done once within a six month period)
 - Tuberculosis screening using the QuantiFERON Gold test
 - Anti-varicella IgG
 - BK virus serum and urine quantitative PCR level
 - Cryoglobulins

After confirmation of eligibility, the PI or otherwise designated AI will contact the Clinical Center Research Pharmacy to randomize the Participant.

8.2 EFFICACY ASSESSMENTS

8.2.1 Clinical Evaluations

Clinical assessments will take place the Dental Clinic, Outpatient Clinic (OP), or 5SWS Day Hospital. Vascular assessments will be performed in the Vascular Lab of the CRC, Salivary assessments will be performed at the Salivary Disorders and Sjögren's syndrome Clinic at the Dental Clinic, Outpatient Clinic 1 (OP1). Subjects will be asked to fast on the day of the appointment and to avoid taking saliva stimulants 24 hours prior to the appointment.

Study Day 1/Visit 2 (on site visit):

- Concomitant medication review
- Drug Accountability- Dispense 35-day supply of study drug
- Vital sign assessments
- Presenting symptoms, abbreviated medical history, and physical examination
- Adverse event review

- Dental History and Oral and Head and Neck examination
- Salivary Collection
- Salivary flow rate
- Oral Microbiome
- Laboratory studies:
 - Complete blood count (CBC) with differential,
 - Serum chemistry panel (creatinine, glucose, urea nitrogen, total bilirubin, alanine aminotransferase, aspartate aminotransferase, alkaline phosphatase, albumin),
 - Pregnancy test (urine or serum; for females of reproductive potential only),
 - Urinalysis and random urine protein/creatinine ratio,
 - BK virus serum and urine quantitative PCR level,
 - Lipid panel: LDH (low density lipoprotein), HDL (high density lipoprotein), TG (Triglycerides), Total cholesterol,
 - Lipoprotein Profile (Apolipoprotein A-1, Apolipoprotein)
 - Lymphocyte pheno-TBNK,
 - Inflammatory markers (hs-CRP, ESR),
 - ANA and anti-ENA panel (anti-RNP, anti-SmRNP, anti-SSA, anti-SSB), anticardiolipin antibodies, lupus anticoagulant, and anti-beta2-glycoprotein antibodies, Anti-ds DNA antibodies,
 - Serum complement components C3 and C4,
 - Quantitative immunoglobulins (IgA, IgG, IgM),
 - Research Labs - 2 red SST, 6 red/green CPT, 1 PAX RNA);
 - Anti-SARS-CoV-2 antibodies
- Mechanistic studies: (intracellular signaling molecules, cytokine expression, circulating immune cell types and autoreactive B cells) – All samples will be run simultaneously for each assay at the end of the study
- Assessment of SS disease activity (ESSDAI, PGA)
- Vascular function studies:
 - Peripheral Wave Analysis (SphygmoCor)
 - Peripheral Arterial Tonometry (Endopat)
 - Cardio-ankle vascular index (CAVI)
- Patient questionnaires (ESSPRI, Dry Mouth Questionnaire, OHIP-14, Xerostomia VAS, FSS, PROMIS-57, SF-36, AECG Symptom Questionnaire)
- Study drug administration:
 - A 35-day supply of study drug or placebo will be dispensed to participants on study day 1 with instructions regarding twice daily dosing regimen and a review of potential side effects. No drug will be dispensed to a female participant of reproductive potential until negative pregnancy test results (serum or urine) have been obtained within 24 hours.

Abbreviated Title: Tofacitinib in Sjögren's syndrome

Version Date: 07/01/2024

- For acute infection(s) requiring antibiotics discovered on Day 1: Any participant found to have an acute infection at baseline visit (Day 1 visit) will have the study drug withheld and their next visit will be scheduled for no more than 30 days later;
- Infections prior to 14 days of Day 1: study medication may be administered
- Between -14 to Day 1: study drug will be delayed up to the upper limit of 45 days from screen date
- If the above stated 14 days puts the patient beyond the limits of protocol mandated pre-screening interval, the participant will be excluded from study participation and then give the opportunity to be re-evaluated and re-enrolled.
- If the infection resolves, study medication will be started. If infection does not resolve within 30 days the participant will be removed from the study
- If a medically significant abnormal lab result (i.e., complete blood count, serum chemistries, pregnancy test, urinalysis and random urine protein/creatinine ratio) occurs at baseline (Day 1 visit), requiring repeat for confirmation, the study drug will be withheld and the next visit will be scheduled no more than 30 days later; if repeat testing reveals resolution of abnormal results, participants will be instructed to begin study medication. If the abnormal lab result does not resolve, participants will be removed from the study. Vascular function studies or research labs will not be repeated.

Study Days 7, 21, 42, 70, 154 (+/- 3 days) Telephone Calls

All participants will receive a telephone call from the study coordinator on study days 7, 21, 42, 70, and 154 (+/- 3 days). These calls will confirm study drug compliance, document any adverse events, and record any new or discontinued concomitant medications. A script with standardized questions will be used to confirm compliance with study drug.

Study Day 14/Visit 3: (on site visit)

All participants will return to the Clinical Center for study day 14 (+/- 7 days); they will be seen in either an outpatient clinic or Day Hospital. The following procedures will be performed at this visit:

- Adverse event assessment
- Concomitant medication review
- Vital sign measurements
- Presenting symptoms, abbreviated medical history and, physical examination
- Laboratory studies:
 - Complete blood count with differential,
 - Serum chemistry panel (creatinine, glucose, urea nitrogen, total bilirubin, alanine aminotransferase, aspartate aminotransferase, alkaline phosphatase, albumin),
 - Pregnancy test (urine or serum; for females of reproductive potential only),

Abbreviated Title: Tofacitinib in Sjögren's syndrome

Version Date: 07/01/2024

- Urinalysis, random urine protein/creatinine ratio,
- BK virus serum and urine quantitative PCR level

Study Days 28 (Visit 4), 56 (Visit 5), 112(Visit 7), 140 (Visit 8)

(on site visits):

All participants will return to the Clinical Center will be seen at the Dental clinic, Outpatient 9 Clinic, or the 5SWS Day Hospital on study days 28, 56,112,140 (all visits +/- 7 days) for a brief visit. Participants will be asked to bring study medication bottle to confirm study drug compliance as well as re-issued of a new 35 day drug supply. The following procedures will be performed at this visit:

- Adverse event assessment
- Concomitant medication review
- Drug accountability-Returning used drug bottle
- Drug accountability- Dispense 35-day supply of study drug
- Vital sign measurements
- Presenting symptoms, abbreviated medical history and physical examination
- Laboratory studies:
 - Complete blood count with differential,
 - Serum chemistry panel (creatinine, glucose, urea nitrogen, total bilirubin, alanine aminotransferase, aspartate aminotransferase, alkaline phosphatase, albumin),
 - Pregnancy test (urine or serum; for females of reproductive potential only),
 - Urinalysis, random urine protein/creatinine ratio
 - Serum complement components C3 and C4,
 - Quantitative immunoglobulins (IgA, IgG, IgM)
 - BK virus serum and urine quantitative PCR level
 - Inflammatory markers (ESR, CRP)
- Assessment of SS disease activity (ESSDAI, PGA)

Study Day 84/Visit 8 (on site visit):

All participants will be seen at the Dental clinic, Outpatient 9 Clinic or the 5SWS Day Hospital on study day 84 (+/- 7 days). They will be asked to bring study medication bottles to assess drug compliance as well as re-issued of a new 35 day study drug supply. Participants will be asked to fast after midnight the night prior for the fasting lipid profile and to avoid taking saliva stimulants 24 hours prior to the appointment. The following procedures will be performed at this visit:

- Adverse event assessment
- Concomitant medication review
- Drug accountability- Returning used drug bottle
- Drug accountability- Dispense 35-day supply of study drug
- Vital sign measurements
- Presenting symptoms, abbreviated medical history and physical examination
- Interim Dental History and Oral, and Head and Neck examination

Abbreviated Title: Tofacitinib in Sjögren's syndrome

Version Date: 07/01/2024

- Ophthalmologic Exam
 - Vision exam,
 - Schirmer's test with/without anesthesia,
 - Ocular surface staining (Fluorescein, Lissamine green)
- Saliva Collection
- Salivary Flow Rate
- Laboratory studies:
 - Complete blood count with differential,
 - Serum chemistry panel (creatinine, glucose, urea nitrogen, total bilirubin, alanine aminotransferase, aspartate aminotransferase, alkaline phosphatase, albumin),
 - Pregnancy test (urine or serum; for females of reproductive potential only),
 - Urinalysis and random urine protein/creatinine ratio,
 - ANA and anti-ENA panel (anti-RNP, anti-SmRNP, anti-SSA, anti-SSB) anticardiolipin antibodies, lupus anticoagulant, and anti-beta2-glycoprotein antibodies, Anti-dsDNA antibodies,
 - Serum complement components C3 and C4
 - Quantitative Immunoglobulins, (IgA, IgG, IgM)
 - Serum protein electrophoresis (SPEP)
 - Inflammatory markers (ESR, CRP)
 - BK virus serum and urine quantitative PCR level
 - Lipid panel: LDH (low density lipoprotein), HDL (high density lipoprotein), TG (Triglycerides), Total cholesterol,
 - Lipoprotein Profile,
 - Lymphocyte pheno-TBNK,
 - Research Labs (2 red SST, 6 red/green CPT, 1 PAX RNA)
- Vascular function studies
 - Peripheral Wave Analysis (SphygmoCor)
 - Peripheral Arterial Tonometry (Endopat)
- Cardio-ankle vascular index (CAVI)Assessment of SS disease activity (ESSDAI, PGA)
- Patient questionnaires (ESSPRI, Dry Mouth Questionnaire, OHIP-14, Xerostomia VAS, FSS, PROMIS-57, SF-36, AECG Symptom Questionnaire)

Study Day 168/Visit 9 (end of treatment visit):

All participants will be seen at the Dental clinic, Outpatient 9 Clinic or the 5SWS Day Hospital on study day 168 (+/- 7 days). Study participants will be asked to return medication bottles to confirm compliance with study drug and to fast overnight for lab tests. Subjects will be asked to avoid taking saliva stimulants 24 hours prior to the appointment.

- Adverse event assessment
- Concomitant medication review
- Drug accountability-Returning used drug bottle
- Vital sign measurements
- Interim Dental History and Oral and Head and Neck examination
- Saliva Collection

Abbreviated Title: Tofacitinib in Sjögren's syndrome

Version Date: 07/01/2024

- Salivary flow rate
- Oral Microbiome Collection
- Ophthalmologic Exam
 - Vision exam
 - Schirmer's test with/without anesthesia
 - Ocular surface staining (Fluorescein, Lissamine green)
 - Pentagraph for tear breakup time, redness scale, tear lake if available
 - MMP-9 simple strip test
- Minor Salivary Gland Biopsy
- Salivary Gland Ultrasound
- Presenting symptoms, abbreviated medical history and physical examination
- Laboratory studies:
 - Complete blood count with differential,
 - Serum chemistry panel (creatinine, glucose, urea nitrogen, total bilirubin, alanine aminotransferase, aspartate aminotransferase, alkaline phosphatase, albumin),
 - Pregnancy test (urine or serum; for females of reproductive potential only),
 - Urinalysis and random urine protein/creatinine ratio,
 - Inflammatory markers (CRP, ESR),
 - ANA and anti-ENA panel (anti-RNP, anti-SmRNP, anti-SSA, anti-SSB), anticardiolipin antibodies, lupus anticoagulant, and anti-beta2-glycoprotein antibodies, Anti-dsDNA antibodies,
 - Serum complement components C3 and C4
 - Quantitative Immunoglobulins, (IgA, IgG, IgM)
 - Serum protein electrophoresis (SPEP)
 - Lipid panel LDL (low density lipoprotein), HDL (high density lipoprotein), TG (triglycerides), total cholesterol
 - Lipoprotein Profile
 - Lymphocyte pheno-TBNK
 - BK virus serum and urine quantitative PCR level
 - Anti-SARS-CoV-2 Antibodies
 - Mechanistic studies: (intracellular signaling molecules, cytokine expression, circulating immune cell types and autoreactive B cells) – All samples will be run simultaneously for each assay at the end of the study
- Assessment of SS disease activity (ESSDAI, PGA, Salivary flow)
- Patient questionnaires (ESSPRI, Dry Mouth Questionnaire, OHIP-14, Xerostomia VAS, FSS, PROMIS-57, SF-36, AECG Symptom Questionnaire)
- EKG
- Assessment of biologic effect
- Assessment of durability of the clinical and biological effects

Study Day 196 (end of study visit):

Abbreviated Title: Tofacitinib in Sjögren's syndrome

Version Date: 07/01/2024

All participants will be seen at the Dental clinic, Outpatient 9 Clinic or the 5SWS Day Hospital. They will be asked to bring their bottles of study drug to account for any remaining study drug at the end of study visit (+/- 7 days). Participants will be asked to fast after midnight the night prior for the fasting lipid profile. Subjects will be asked to avoid taking saliva stimulants 24 hours prior to the appointment. The following procedures will be performed at this visit:

- Adverse event assessment
- Concomitant medication review
- Vital sign measurements
- Interim Dental History and Oral, Head and Neck Exam
- Saliva Collection
- Saliva Flow rates
- Ophthalmologic Exam
 - Vision exam
 - Intraocular pressure (IOP)
 - Schirmer's test with/without anesthesia
 - Ocular surface staining (Fluorescein, Lissamine green)
 - Pentagraph for tear breakup time, redness scale, tear lake (if available)
- Presenting symptoms, abbreviated medical history, and physical examination
- Laboratory studies:
 - Complete blood count with differential,
 - Serum chemistry panel (creatinine, glucose, urea nitrogen, total bilirubin, alanine aminotransferase, aspartate aminotransferase, alkaline phosphatase),
 - Pregnancy test (urine or serum; for females of reproductive potential only),
 - Urinalysis and random urine protein/creatinine ratio,
 - Inflammatory markers (CRP, ESR),
 - ANA and anti-ENA panel (anti-RNP, anti-SmRNP, anti-SSA, anti-SSB) anticardiolipin antibodies, lupus anticoagulant, and anti-beta2-glycoprotein antibodies, Anti-dsDNA antibodies,
 - Serum complement components C3 and C4
 - Quantitative Immunoglobulins, (IgA, IgG, IgM)
 - Serum protein electrophoresis (SPEP)Lipid panel LDL (low density lipoprotein), HDL (high density lipoprotein), TG (Triglycerides), total cholesterol
 - Lipoprotein Profile
 - Lymphocyte pheno-TBNK
 - BK virus serum and urine quantitative PCR level
 - Research Labs (2 red SST, 6 red/green CPT, 1 PAX RNA)
 - Mechanistic studies: (intracellular signaling molecules, cytokine expression, circulating immune cell types and autoreactive B cells) – All samples will be run

simultaneously for each assay at the end of the study

- EKG
- Assessment of SS disease activity (ESSDAI, PGA)
- Patient questionnaires (ESSPRI, Dry Mouth Questionnaire, OHIP-14, Xerostomia VAS, FSS, PROMIS-57, SF-36, AECG Symptom Questionnaire).
- Vascular function studies
 - Peripheral Wave Analysis (SphygmoCor)
 - Peripheral Arterial Tonometry (Endopat)
 - Cardio-ankle vascular index (CAVI)
- Assessment of biologic effect
- Assessment of durability of the clinical and biological effects

Unscheduled Visits:

In the event of an adverse event or other reason that results in an unscheduled visit and will take place at the Dental clinic, Outpatient 9 Clinic, the 5SWS Day Hospital. Clinically appropriate assessments from the list below will be completed at the discretion of the principal investigator and medically responsible investigator at this visit:

- Adverse event assessment (AE)
- Concomitant medication review
- Vital sign measurements
- Medical history and physical examination
- Laboratory studies
 - Complete blood count with differential,
 - Serum chemistry panel (creatinine, glucose, urea nitrogen, total bilirubin, alanine aminotransferase, aspartate aminotransferase, alkaline phosphatase)
 - Pregnancy test (urine or serum; for females of reproductive potential only)
 - Urinalysis and random urine protein/creatinine ratio,
 - Inflammatory markers (CRP, ESR),
 - anti-ENA (Sm, RNP, SSA, SSB), serum complement components C3 and C4
 - Quantitative Immunoglobulins (IgA, IgG, IgM)
 - Serum protein electrophoresis (SPEP)
 - Lipid panel LDL (low density lipoprotein), HDL (high density lipoprotein), TG (Triglycerides), total cholesterol
 - Lipoprotein Profile
 - Lymphocyte pheno-TBNK
 - BK virus serum and urine quantitative PCR level
 - Research Labs (2 red SST, 6 red/green CPT, 1 PAX RNA)
- EKG
- Assessment of SS disease activity (ESSDAI, PGA)

Abbreviated Title: Tofacitinib in Sjögren's syndrome

Version Date: 07/01/2024

- Patient questionnaires (ESSPRI, Dry Mouth Questionnaire, OHIP- 14, Xerostomia VAS, FSS, PROMIS-57, SF-36, AECG Symptom Questionnaire)
- Drug accountability

8.2.2 Follow-up/Termination Procedures:

While on this study, participants will continue to receive regular medical care from their primary physicians. Any AEs reported will be followed by the investigators as described in Section 16.1.8. Following completion of the study or after withdrawal from the study, participants will return to the care of their referring physicians. Participants may continue their follow up visits on protocol 15-D-0051 as appropriate. A summary of the participants' course in the study will be sent to the referring physician.

Participants who withdraw or are withdrawn from the study after receiving study treatment will be asked to complete the day 168 and 196 for close out safety assessments. Participants are deemed ineligible before study day 1 or randomization will resume care with their referring physician with no further evaluation in this protocol.

